### **Seventh Secondary Endpoint**

The distribution of this endpoint is continuous. The primary population for analysis of this endpoint will be the FAS population. The estimates will be derived using a mixed model repeated measure procedure; the 12 week result will be the principal time point of interest.

Time in range, glucose variability by continuous glucose monitoring (CGM)

### **Eighth Secondary Endpoint**

The distribution of this endpoint is binary. The analysis will be based on the proportion of patients that meet the endpoint at 24 weeks post-procedure. The primary population for analysis of this endpoint will be the FAS population.

Proportion of treated patients with an HbA1c improvement of  $\geq 0.5\%$  from baseline at 24 weeks (24 week score minus baseline score). Patients who fail to have HbA1c improvement of  $\geq 0.5$  points from baseline, for any reason, will be counted as not having achieved this endpoint.

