12.4 Statistical Analysis

12.4.1 General Statistical Considerations

Analyses will be performed according to the general principles and directions outlined in these methods.

- Continuous data will be summarized using descriptive statistics: mean, standard deviation, median and range or interquartile range. Categorical variables will be summarized using frequency counts and percentages.
- For events which can occur multiple times in a single subject (e.g., adverse events), summaries
 will be comprised of the number and percentage of subjects with an event and the total number of
 such events. The proportion of subjects with events will be considered primary for analysis
 purposes.
- In general, available data will be used for all analyses, and missing data will not be replaced or
 otherwise imputed in summaries and analyses of study outcomes. However, to avoid biasing
 results due to confounding therapies, effectiveness data collected after an identified initiation of
 rescue medication for hyperglycemia will be replaced by the last value collected prior to such
 rescue intervention.
- Although the study is not explicitly powered to test *a priori* statistical objectives, comparisons citing p-values may be made between baseline metrics to values collected post-intervention, and between subgroups including the two treatment arms. In such cases, p-values will be presented using two-sided tests at a 0.05 level of significance or equivalently one-sided tests at a 0.025 level of significance.

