### 6. ANALYSIS POPULATIONS

Patients will be considered enrolled in the study once the patient has passed endoscopic screening. Screen failures are defined as patient who consented to participate in the clinical study and started the screening tests specified by the protocol but are not subsequently enrolled in the study.

The primary and secondary safety analyses will be performed using the ITT. The primary effectiveness analyses will be performed using the FAS population. The Per-Protocol population and Completed-Cases population will be used for the sensitivity analyses of the primary and secondary effectiveness endpoints.

*Intent-to-Treat*: The Intent-to-Treat population includes all enrolled patients, regardless of the patient having received the target treatment (at least 6cm of duodenum treated). The point of enrollment occurs when a patient has provided written informed consent and an energy delivery has been attempted during the index procedure.

*Full Analysis Set*: The FAS population consists of the ITT population patients who received the target treatment (at least 6 cm of duodenum treatment) and that have at least one post-treatment follow-up examination.

**Per-Protocol**: The Per-Protocol population is a subset of the FAS population and includes all patients who received the target treatment, do not have any major eligibility violations, and maintained stable glucose-lowering medications for 24 weeks post-procedure. The definition of what constitutes a major eligibility violations will be established before the study database is locked.

**Completed Cases**: The Completed Cases population is a subset of the Per-Protocol population and includes all patients who received the target treatment, do not have any major eligibility violations, and maintained stable glucose-lowering medications for 24 weeks post-procedure, and completed the final Week 48 End of Study Visit.

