### Change = Post- Procedure value - baseline value.

- Missing data may have an impact upon the interpretation of the trial data. However, given the feasibility nature of this study, coupled with the number of patients within a Comparison Set, multiple imputation will not be attempted. The primary presentation of the results will be based on the observed data. A methodology is defined in this section for addressing missing dates.
- Date variables will be formatted as DDMMMYYYY for presentation; SAS Date9. format.
- Months will be converted to days by dividing by 30.42 and rounding up to achieve an integer value.
- SAS® Version 9.4 will be the statistical software package used for all data analyses.
- All data from this study will be presented in a listing.
- Table and listing numbering will follow ICH guidelines for post-text table and listing numbering.

For Adverse Event reporting, which includes primary and secondary variables, the primary analysis will be based on Patient counts (e.g., the number and percentage of Patients with events among the total number of Patients). The data will be presented in the format of p% (x/N) [e], with p and x being the percentage and number of Patients with events, respectively, N being the sample size of the analysis population, and e being the total number of events occurred in the x Patients. Asymptotic confidence limits will be presented based on the normal approximation to the binomial distribution for differences in proportions. Exact confidence intervals will be used for all other presentations.

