# 7.3. Handling of Missing Data

# 7.3.1. Missing and Censored Data

All tabulations and analyses will be based on the observed data without imputation, with the exception of dates.

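### The SAP allows two denominators for the Week 24 HbA1c responder proportion (the whole FAS, or only patients with a Week 24 value) and does not say which rule governs

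*SAP*

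**What the plan says.** **The endpoint rule.** SAP section 9 (Eighth Secondary Endpoint) treats the endpoint as binary: "The analysis will be based on the proportion of patients that meet the endpoint at 24 weeks post-procedure". The population is the FAS. Patients without the required improvement "from baseline, for any reason, will be counted as not having achieved this endpoint". The shorter definitions of this endpoint in SAP 4.2.1 and 9.2 do not carry that sentence.

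**The population.** SAP section 6 builds the FAS from patients who received the target treatment and "that have at least one post-treatment follow-up examination". A Week 24 HbA1c is not a condition of entry.

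**The general rule in the SAP.** Section 7.3.1 states: "All tabulations and analyses will be based on the observed data without imputation, with the exception of dates". Section 7, where it rules out multiple imputation, adds: "The primary presentation of the results will be based on the observed data".

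**The protocol.** Section 12.4.1 is softer. As a general matter, it says, analyses use whatever was collected, and gaps are not filled in, nor "otherwise imputed in summaries and analyses of study outcomes". It mentions no exception for dates. It then makes an exception of its own: effectiveness data collected after the start of "rescue medication for hyperglycemia will be replaced by the last value collected prior to such" intervention. The SAP does not repeat that rule.

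**The concern.** A programmer working from SAP section 9 would keep an FAS patient with no Week 24 HbA1c in the denominator as a failure. A programmer working from SAP 7.3.1 would leave that patient out. Both could point to the text, and the table would carry the same label, a share of treated patients, either way.

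The choice works in one direction. For a fixed number of responders, removing patients with missing values can only raise the proportion or leave it unchanged. If patients who left early did worse than those who stayed, the observed-data version favours the device. The study is open-label, so an unsettled rule could be settled after results are visible. The documents do not say that this would happen.

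The post-rescue rule raises a related problem. Under protocol 12.4.1, a rescued patient's responder status comes from the last HbA1c before rescue. Under SAP 7.3.1 as written, it comes from the value observed at Week 24, on rescue medication.

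**Working it through.** The documents give no expected responder rate, dropout rate or power calculation for this endpoint, so there is no planned figure to reproduce. The check has two parts: whether the two rules can diverge, and by how much.

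**1. Can they diverge?** They diverge only if someone in the FAS has no Week 24 HbA1c.
- FAS entry needs the target treatment and one later follow-up (SAP 6), so an early leaver can be in it.
- Participants who exit early are not replaced (protocol 8.2).
- A participant leaving before Week 24 should, where possible, have HbA1c measured at a discontinuation visit (protocol 7.13.6). That visit may fall outside days 152 to 184, the expanded Week 24 window in SAP 8.6.

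Missing Week 24 values are therefore possible but not certain.

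**2. By how much?** Inputs:
- From the documents: N = 20 patients, in groups of 3, 7 and 10 (SAP 3; 3 + 7 + 10 = 20).
- Assumed: all 20 are in the FAS; r responders, 8 to 12 of 20; m patients missing at Week 24, 1 to 4.

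Formulas:
- Endpoint rule (SAP 9): r / N
- Observed-data rule (SAP 7.3.1): r / (N − m)
- Gap: r / (N − m) − r / N = r·m / [N(N − m)], which is never negative

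All patients, N = 20, r = 10 (exact 95% intervals for selected rows):

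| Missing m | Endpoint rule | Observed data only | Gap (points) |
|---|---|---|---|
| 0 | 10/20 = 50.0% (27.2 to 72.8) | 10/20 = 50.0% | 0 |
| 1 | 50.0% | 10/19 = 52.6% | 2.6 |
| 2 | 50.0% | 10/18 = 55.6% (30.8 to 78.5) | 5.6 |
| 3 | 50.0% | 10/17 = 58.8% | 8.8 |
| 4 | 50.0% | 10/16 = 62.5% (35.4 to 84.8) | 12.5 |

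With r between 8 and 12, the gap runs from 2.1 to 3.2 points with 1 missing, 4.4 to 6.7 with 2, and 10.0 to 15.0 with 4.

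By treatment group (responder counts assumed):

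| Group | Endpoint rule | Observed, 1 missing | Observed, 2 missing |
|---|---|---|---|
| 750 V double, N = 10, r = 5 | 50.0% | 5/9 = 55.6% | 5/8 = 62.5% |
| 600 V double, N = 7, r = 4 | 57.1% | 4/6 = 66.7% | 4/5 = 80.0% |
| 600 V single, N = 3, r = 1 | 33.3% | 1/2 = 50.0% | 1/1 = 100% |

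**The case against.** **The specific rule should govern the general one.** This is the strongest reply. The sentence in SAP section 9 is written for this endpoint, and classing a patient as not having met an endpoint is arguably a definition rather than an imputed HbA1c. The SAP uses the same any-reason wording for procedure success and for the ninth endpoint, which looks like a deliberate convention. I think this is probably the intent, and the fix adopts it. But the SAP does not say so. Section 7.3.1 covers every tabulation and lists one exception, which is not this one. Elsewhere (SAP 8.2, 8.3 and 8.5) patients with missing data are dropped from the table.

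**Missing values are never named.** This stands. That a missing Week 24 value counts as failure is inferred from the any-reason wording. It is the natural reading, but not an express rule.

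**Missing data may be few.** This also stands. Home blood sampling (protocol 7.13.4), completing Week 24 activities before rescue (6.2.3) and the discontinuation visit all reduce the loss. None guarantees a Week 24 value. SAP 7 also puts all data in listings, so a careful reader could recompute either proportion.

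**Stronger readings that the documents do not support.**
- A reader might infer that the protocol also bars all imputation except for dates. It does not: its rule applies in general, it says nothing about dates, and it requires a substitution after rescue.
- A reader might take this proportion for the study's main result. It is the eighth of 18 secondary endpoints; the primary endpoint is safety, protocol section 3 describes efficacy as exploratory, and SAP section 9 plans no formal hypothesis tests.
- A reader might want one whole-FAS denominator for every HbA1c responder endpoint. That would contradict the ninth endpoint, which leaves out patients who did not respond at Week 24.

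**Conclusion.** The concern holds within the SAP. The endpoint rule in section 9 and the observed-data rule in sections 7 and 7.3.1 give different denominators for the Week 24 responder proportion, and no order of precedence is stated.

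The size depends on how many FAS patients lack a Week 24 HbA1c, which the documents do not give. Under the assumed counts it is 50.0% against 55.6% with 2 of 20 missing and 50.0% against 62.5% with 4 missing. It is proportionally larger in the small groups, and zero if nobody is missing. These gaps sit inside wide intervals (27.2% to 72.8% for 10 of 20). What is at stake is a clear and fixed reporting rule for a descriptive result; no test decision depends on it.

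The protocol's post-rescue substitution, absent from the SAP, is a second unsettled input to the same classification. The primary safety endpoint is not affected.

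**What to change.** Amend SAP 7.3.1 so that its exceptions are dates and the two HbA1c responder endpoints, as follows:
- **Eighth endpoint:** an FAS patient with no Week 24 HbA1c is classed as not having met the endpoint, and all FAS patients stay in the denominator.
- **Ninth endpoint:** a Week 24 responder with no Week 48 HbA1c is classed as not having maintained the improvement. The denominator remains the Week 24 responders, as section 9 already has it.

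Then:
- Repeat the rule in SAP 4.2.1 and 9.2, so that every definition of these endpoints agrees.
- Add the observed-case proportion, with its n, as a labelled sensitivity row.
- Reconcile the SAP with protocol 12.4.1 on effectiveness data collected after rescue, so that it is clear which HbA1c value classifies a rescued patient.

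The cost is a few sentences and an extra table row, with no new data. The small downside is a slightly less favourable responder rate than observed cases alone would give, if any values are missing.

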### **Ninth Secondary Endpoint**

The distribution of this endpoint is binary. Proportion of treated patients who achieve a HbA1c improvement of  $\geq 0.5\%$  or more at 24 weeks from baseline and maintained at 48 weeks. Patients who fail to maintain HbA1c improvement  $\geq 0.3\%$  at 48 weeks, for any reason, will be counted as not having achieved this endpoint. Patients who fail to achieve a HbA1c  $\geq 0.5\%$  at 24 weeks will be excluded from the tabulation. The primary population for analysis of this endpoint will be the FAS population.

Proportion of treated patients with an HbA1c improvement  $\geq 0.5\%$  from baseline at 24 weeks maintained at 48 weeks.

**Tenth Secondary Endpoint:** The distribution of this endpoint is continuous. The primary population for analysis of this endpoint will be the FAS population. Change in weight from baseline (post-baseline minus baseline) by visit. Weight change will be reported in both kilograms and %TBWL.

**Eleventh Secondary Endpoint:** Change in glucose-lowering medication usage.

**Twelfth Secondary Endpoint:** The distribution of this endpoint is continuous. The primary population for analysis of this endpoint will be the FAS population. Change in liver enzyme from baseline at 24 weeks (post-baseline minus baseline) for Alanine Aminotransferase (ALT).

**Thirteenth Secondary Endpoint:** The distribution of this endpoint is continuous. The primary population for analysis of this endpoint will be the FAS population. Change in liver enzyme from baseline at 24 weeks (post-baseline minus baseline) for Aspartate Aminotransferase (AST).

Version 1.0 Confidential Page 31 of 42

**Fourteenth Secondary Endpoint:** The distribution of this endpoint is continuous. The primary population for analysis of this endpoint will be the FAS population. Change from baseline in blood pressure by visit (systolic and diastolic run separately).

**Fifteenth Secondary Endpoint:** The distribution of this endpoint is continuous. The primary population for analysis of this endpoint will be the FAS population. Change in lipid profile from baseline by visit: total cholesterol

**Sixteenth Secondary Endpoint:** The distribution of this endpoint is continuous. The primary population for analysis of this endpoint will be the FAS population. Change in lipid profile from baseline by visit: triglycerides

**Seventeenth Secondary Endpoint:** The distribution of this endpoint is continuous. The primary population for analysis of this endpoint will be the FAS population. Change in lipid profile from baseline by visit: HDL

**Eighteenth Secondary Endpoint:** The distribution of this endpoint is continuous. The primary population for analysis of this endpoint will be the FAS population. Change in lipid profile from baseline by visit: LDL

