Secondary Endpoints	 Procedure success rate defined as the proportion of participants who successfully received the target treatment of at least 6 cm of duodenum treatment Procedure time defined as the time between the Endogenex catheter insertion and catheter removal. Change from baseline in glycemic parameters post procedure by visits HbA1c Fasting plasma glucose (FPG) Insulin resistance by HOMA-IR Post prandial plasma glucose (PPG), Beta cell function, disposition index by mixed meal tolerance test (MMTT) Time in range, glucose variability by continuous glucose monitoring (CGM) Proportion of treated participants with an HbA1c improvement ≥0.5 points from baseline at 24 weeks Proportion of treated participants with an HbA1c improvement ≥0.5 points from baseline at 24 weeks and maintained at 48 weeks Change in weight from baseline by visit Change in glucose-lowering medication usage Change in liver enzymes from baseline at 24 weeks Alanine Aminotransferase (ALT) Aspartate Aminotransferase (AST) Change from baseline in blood pressure and lipid profile by visit 		
Safety Evaluation	Safety will be characterized through a summary of the incidence of adverse events, device- or procedure-related adverse events, and serious device- or procedure-related		
	adverse events.		
Inclusion Criteria	1. 22-65 years of age		
	2. Current diagnosis of T2D3. History of T2D for at least 3 years and less than or equal to 10 years		
	3. History of T2D for at least 3 years and less than or equal to 10 years		

- 4. HbA1C of 7.5-10.0%, inclusive
- 5. BMI 24-40 kg/ m^2 , inclusive
- 6. On two to three non-insulin glucose lowering mediations, with one at maximum tolerated dose and another at half-maximum dose at least, with no changes in medication for at least 12 weeks prior to baseline visit prior to baseline visit
- 7. History of failed attempt to reach glycemic goal by lifestyle modifications
- 8. Weight stability (defined as a < 5% change in body weight) for at least 12 weeks prior to the screening visit
- 9. Agree not to donate blood during participation in the study.
- 10. Able to comply with study requirements and understand and sign the Informed Consent Form
- 11. Women of childbearing potential must be using an acceptable method of contraception throughout the study
- 12. Willing and able to use CGM for the duration of the study and comply with study visits and study tasks as required per protocol.

13.

Exclusion Criteria

- 1. Diagnosed with type 1 diabetes

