3 STUDY OBJECTIVES AND ENDPOINTS

The objective of this FIH study is to assess the feasibility and preliminary safety of the Endogenex Device for endoscopic duodenal mucosal regeneration in individuals with type 2 diabetes inadequately controlled on 2-3 non-insulin glucose-lowering medications.

The study will also assess, as exploratory endpoints, treatment efficacy, evaluated by changes in glycemic control and liver enzymes post procedure from baseline.

Objectives	Endpoints
Primary	
To assess the safety of the Endogenex Device for DMR procedure	Proportion of participants experiencing one or more device- or procedure-related serious adverse events at 12 weeks post procedure.
Secondary	
To assess the technical feasibility of the Endogenex Device for DMR procedure	 Procedure success: defined as successful treatment of at least 6 cm of duodenum segment. Procedure time: defined as the time between the Endogenex catheter insertion and the catheter removal.
To assess changes in glycemic control	 Change from baseline in glycemic parameters post index procedure, by visits
To assess changes in liver enzymes	 HbA1c Fasting plasma glucose (FPG) Insulin-resistance by HOMA-IR Post prandial plasma glucose (PPG), Beta cell function, disposition index by mixed meal tolerance test (MMTT) Time in range, glucose variability by continuous glucose monitoring (CGM) Proportion of treated participants with an HbA1c improvement of 0.5% or more at 24 weeks from
	 Proportion of treated participants with an HbA1c improvement of 0.5% or more at 24 weeks from baseline and maintained at 48 weeks Change in weight from baseline by visit Change in glucose-lowering medication usage Change in liver enzyme from baseline at 24 weeks Alanine Aminotransferase (ALT)

	o Aspartate Aminotransferase (AST)
•	Change from baseline in blood pressure and lipid profile by visit

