**Eighth Secondary Endpoint:** Proportion of treated patients with an HbA1c improvement of ≥0.5% points from baseline at 24 weeks (24 week value minus the baseline value).

**Ninth Secondary Endpoint:** Proportion of treated participants with an HbA1c improvement of ≥0.5 points or more at 24 weeks from baseline and maintained at 48 weeks.

Note: Proportion of treated patients who achieve a HbA1c improvement of  $\geq 0.3\%$  or more at 24 weeks from baseline and maintained at 48 weeks. Patients who fail to maintain HbA1c improvement  $\geq 0.5\%$  at 48 weeks, for any reason, will be counted as not having achieved this endpoint. Patients who fail to achieve a HbA1c  $\geq 0.5\%$  improvement at 24 weeks will be excluded from the tabulation.

**Tenth Secondary Endpoint:** Change in weight from baseline (post-baseline minus baseline) by visit. Weight change will be reported in both kilograms and %TBWL.

Eleventh Secondary Endpoint: Change in glucose-lowering medication usage.

**Twelfth Secondary Endpoint:** Change in liver enzyme from baseline at 24 weeks (post-baseline minus baseline) for Alanine Aminotransferase (ALT).

**Thirteenth Secondary Endpoint:** Change in liver enzyme from baseline at 24 weeks (post-baseline minus baseline) for Aspartate Aminotransferase (AST).

Fourteenth Secondary Endpoint: Change from baseline in blood pressure by visit (systolic and diastolic run separately).

Fifteenth Secondary Endpoint: Change in lipid profile from baseline by visit: total cholesterol

Version 1.0 Confidential Page 13 of 42

Sixteenth Secondary Endpoint: Change in lipid profile from baseline by visit: triglycerides

Seventeenth Secondary Endpoint: Change in lipid profile from baseline by visit: HDL

Eighteenth Secondary Endpoint: Change in lipid profile from baseline by visit: LDL

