### **Binary Variable Assessed at a Single Time Point (3 endpoints):**

- **Secondary Endpoint:** Procedure success: defined as successful treatment of at least 6 cm of duodenum segment.
- **Secondary Endpoint:** Proportion of treated patients with an HbA1c improvement of  $\geq 0.5\%$  from baseline at 24 weeks (24 week score minus baseline score).
- **Secondary Endpoint:** Proportion of treated patients with an HbA1c improvement of >0.5% from baseline at 24 weeks maintained at 48 weeks.

For each set of results for each Comparison Set, the following 2 research questions will be addressed. Results will be presented using the Level 1 tables b through e.

For the endpoints measured on a binary scale, what are the overall estimates in the FAS population.

For the endpoints measured on a binary scale, is there a difference in the estimates in the FAS population based on the generation of the device, voltage, and single vs. double treatment?

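### The endpoint for HbA1c response maintained at 48 weeks drops Week 24 non-responders from its denominator and mixes 0.3 and 0.5 thresholds, so it no longer estimates the protocol's proportion of treated participants

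*SAP*

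**What the plan says.** Protocol Summary, Secondary Endpoints: "Proportion of treated participants with an HbA1c improvement ≥0.5 points from baseline at 24 weeks and maintained at 48 weeks". Protocol section 3 says the same: "Proportion of treated participants with an HbA1c improvement of 0.5% or more at 24 weeks from baseline and maintained at 48 weeks". Neither place removes participants who did not respond at Week 24, and neither mentions 0.3. Protocol section 12.4.4 assigns the secondary endpoints to the mITT population (the SAP's FAS), which section 12.3 defines by treatment received and follow-up, not by response.

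The SAP describes the endpoint in several places:

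- **Section 9, Ninth Secondary Endpoint.** Requires at least 0.5 at Week 24. The failure rule at Week 48 reads "Patients who fail to maintain HbA1c improvement $\geq 0.3\%$ at 48 weeks". Those below 0.5 "at 24 weeks will be excluded from the tabulation". The named population is the FAS.
- **Section 4.2.1, Note to the Ninth Secondary Endpoint.** Gives at least 0.3 at Week 24 and at least 0.5 at Week 48, then says that those who miss a 0.5 "improvement at 24 weeks will be excluded from the tabulation".
- **Section 9.2, binary endpoints.** "Proportion of treated patients with an HbA1c improvement of >0.5% from baseline at 24 weeks maintained at 48 weeks". It states no exclusion and asks for estimates and group differences in the FAS.
- **Section 9.2, list of top-line tables.** Table 14.4.4 summarises HbA1c improvement by visit at 0.3 points or more.

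For the Eighth Secondary Endpoint (response at Week 24), section 9 keeps failures for any reason in the denominator as not achieved.

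**The concern.** A proportion of treated patients and a proportion of responders who stay responders answer different questions. The protocol asks the first. The SAP text computes the second and keeps the first one's name. A device that helped two of 20 patients, and kept both, would score 100% on an endpoint labelled as a share of treated patients.

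Two further consequences follow. The SAP compares groups of 3, 7 and 10 patients, and under this rule each group is first cut to a subset chosen by its own outcome, so the groups being compared are no longer the treated groups. The endpoint also cannot be programmed unambiguously: sections 4.2.1 and 9 place 0.3 and 0.5 at opposite visits, so two programmers could reach different counts from the same data, and the choice between them could be made after the results are seen. SAP section 3 allows the planned analyses to go into regulatory submissions and manuscripts.

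**Working it through.** **Inputs from the documents.** Total N = 20, tabulated in SAP section 3 as 3 + 7 + 10 = 20; this is the largest possible FAS. The endpoint definitions are those set out above. The documents state no expected rate or power for this endpoint, so there is no planned figure to reproduce.

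**Inputs assumed.** Week 24 responders, Week 48 maintenance, SD and correlation are not given, so ranges are used.

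**Denominator.** Let N be the FAS size, r the number with at least 0.5 improvement at Week 24, and m the number of those who maintain at Week 48.

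- Protocol: m/N
- SAP: m/r
- Ratio, SAP to protocol: (m/r) / (m/N) = N/r

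The ratio exceeds 1 whenever r < N, and the two rates differ whenever m is also above 0. With N = 20 and exact (Clopper-Pearson) 95% intervals:

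| r | m | Protocol m/N | SAP m/r | N/r |
|---|---|---|---|---|
| 8 | 6 | 6/20 = 30% (11.9 to 54.3) | 6/8 = 75% (34.9 to 96.8) | 2.50 |
| 10 | 7 | 7/20 = 35% (15.4 to 59.2) | 7/10 = 70% (34.8 to 93.3) | 2.00 |
| 12 | 9 | 9/20 = 45% (23.1 to 68.5) | 9/12 = 75% (42.8 to 94.5) | 1.67 |
| 16 | 12 | 12/20 = 60% (36.1 to 80.9) | 12/16 = 75% (47.6 to 92.7) | 1.25 |

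An SAP result of 75% is therefore compatible with anything from 30% to 60% of FAS patients when 8 to 16 respond. In the single-treatment group of 3, one responder who maintains gives 1/1 = 100% in place of 1/3 = 33%.

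**Threshold.** The two SAP versions act differently.

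- *Section 4.2.1:* 0.3 at Week 24 has no effect, because anyone below 0.5 at Week 24 is excluded anyway. Week 48 stays at 0.5.
- *Section 9:* the Week 48 bar falls to 0.3, so more responders count as maintaining.

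To size the second effect, improvements at Weeks 24 and 48 were taken as bivariate normal, with assumed mean 0.9 at Week 24, SD 1.0 at both visits and correlation 0.7. The probability of at least 0.5 at Week 24 is then P(Z ≥ (0.5 − 0.9)/1.0) = 65.5%. The conditional rate is the joint rate divided by 65.5%.

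| Assumed Week 48 mean improvement | Protocol (joint, 0.5 at both visits) | Conditional, 0.5 at Week 48 | Conditional, 0.3 at Week 48 |
|---|---|---|---|
| 0.6 | 47% | 71% | 79% |
| 0.9 | 54% | 82% | 88% |

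Over a wider set of assumptions (mean improvement 0.5 or 0.9 at both visits, SD 0.8 to 1.2, correlation 0.5 to 0.7), moving the Week 48 bar from 0.5 to 0.3 adds about 5 to 9 percentage points to the conditional rate. The exclusion is the larger of the two effects.

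**The case against.** The strongest case concerns weight. This is the ninth of 18 secondary endpoints in a 20-patient feasibility study with a safety primary endpoint. Protocol section 3 calls efficacy exploratory, and SAP sections 7.1 and 9 disclaim formal testing. The exclusion is stated openly, the Eighth endpoint gives the Week 24 rate over the whole FAS, and counts accompany percentages, so a careful reader could rebuild m/N. That is fair, and it limits the harm. It does not make the labelled estimate correct, and in a descriptive study the estimate is the result.

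Several narrower points stand:

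- Only section 9's use of 0.3 raises the rate.
- The strict inequality in section 9.2 may be a lost underline in the text extraction, so little should rest on it.
- Table 14.4.4 is not explicitly tied to this endpoint. Its 0.3 is unexplained, and its purpose has to be confirmed.
- The protocol gives no separate Week 48 number. Reading maintained as still at least 0.5 is the natural sense, but it is a reading.
- The example with 10 responders doubles the rate. The bivariate normal illustration implies 65.5% response, for which the denominator effect is 1/0.655 = 1.53-fold.
- Medication is optimised after Week 24 under the protocol, so Week 48 HbA1c reflects added drugs as well as the device under either denominator. Correcting the denominator does not remove that limit on interpretation.

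None of these restores the protocol's denominator or reconciles the swapped thresholds.

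**Conclusion.** The concern holds. Followed as written, the SAP reports m/r where the protocol defines m/N, and sections 4.2.1 and 9 contradict each other on thresholds. The overstatement factor is N/r: 2.5 to 1.25 for an assumed 8 to 16 responders of 20. Under the illustrative model with correlation 0.7, a protocol rate of 47% to 54% would appear as 79% to 88% under section 9. These sizes rest on assumed response rates, SD and correlation. The direction needs only one non-responder in the FAS and one responder who maintains. It must be fixed before analysis, because the number produced would not be the endpoint the protocol names.

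**What to change.** In SAP sections 4.2.1, 9 and 9.2:

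1. Use all FAS patients as the denominator and delete the exclusion of Week 24 non-responders.
2. Define success as an improvement of at least 0.5 at Week 24 and at least 0.5 at Week 48, with the same inequality sign throughout, and remove 0.3.
3. Count a patient who fails at either visit, or whose value is missing at either visit, as not having achieved the endpoint. This matches the Eighth endpoint's rule and settles how a missing Week 24 value is handled, which the SAP leaves open.
4. Correct Table 14.4.4 to 0.5. If a 0.3 summary is meant for some other purpose, say so and list a separate 0.5 table. As listed, no top-line responder table uses the protocol's threshold.
5. If durability among Week 24 responders is wanted, report it as a supplementary summary under its own name, with its own n.

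The cost is SAP wording and table titles. No new data are needed. The stated rate will be less favourable.
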